7.9.5 Subgroup Analysis

The following subgroup analyses will be performed for the clinical outcome composite endpoint and for the valve function composite endpoint at 12 months:

- 1. Age (<75, ≥ 75 years)
- 2. Sex (female, male)
- 3. STS-PROM (<3, 3-5, 5-8, >8%)
- 4. Baseline left ventricular ejection fraction (LVEF) (< 50%, \geq 50%)
- 5. Renal dysfunction (on dialysis) vs. not on dialysis at time of screening
- 6. History of atrial fibrillation (AF)
- 7. Prior cerebrovascular accident (CVA)
- 8. Pre-existing left bundle branch block (LBBB) / complete heart block (CHB)

For each subgroup, the incidence of the composite endpoint will be presented with the Kaplan-Meier estimate of the composite event rate at 365 days (cumulative incidence) within treatment arm along with the estimated difference in event rates (SE TAV - BE TAV) at 365 days and corresponding two-sided 95% large sample confidence interval. Additionally, p-values testing for interaction between treatment and subgroup will be computed using a Cox proportional-hazards model. The same approach will be used for the clinical outcome composite endpoint and valve function composite endpoint.

Additionally, analyses by sex will be performed for the powered secondary endpoint.

7.10 Safety Evaluation

CEC adjudicated adverse events will be summarized at 30 days, 1 year, and annually through 5 years. The number of events, number of subjects with event, and the Kaplan-Meier event rate (cumulative incidence) will be reported for each category and time point by treatment arm.

Additionally, a summary of procedure related adverse events, and device related adverse events will be reported by MedDRA system organ class and preferred term by treatment arm. Device deficiencies including deficiencies which could have led to a serious adverse device effect and listing of subject deaths will also be reported.

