7.2 General Methodology

Descriptive statistics of continuous outcomes will be presented by treatment arm and include count, mean, median, standard deviation, first and third quartiles, minimum and maximum. For categorical outcomes, the number and percentage of subjects in each category will be presented by treatment arm.

For time-to-event outcomes using Kaplan-Meier methods, the time points of 30 days, 1 year, 2 years, 3 years, 4 years, and 5 years will correspond to 30, 365, 730, 1095, 1460, and 1825 days post-implant, respectively. For each applicable time point, the event or event-free rate, the number of subjects at risk, the number of subjects with an event, the Greenwood standard error of the estimate, and the log-log transformed 95% confidence interval using the Greenwood standard error will be reported. For subjects with an event, the date of event will be based on the first event occurrence. For subjects without an event, date of censoring will be based on the latest of all follow-up visits, assessments, and events (for non-death events). Methods which account for interval censoring may be considered for survival analysis of events based on echo assessment.

For analyses using echocardiographic data, only echo data corresponding to the implanted study valve will be used; data post-explant or after reintervention will be excluded from analysis.

SMART Trial Statistical Analysis Plan Form Revision 5.0 Page 14 of 27 Mectronic

Subject data listings and tabular and graphical presentations of results will be provided. Unless otherwise specified, a two-sided 0.05 level of significance will be used to declare treatment arms significantly different.

All statistical analyses will be performed using SAS version 9.4 or higher (SAS Institute, Cary, North Carolina, USA) or other widely accepted statistical or graphical software.

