7.4 Handling of Missing, Unused, and Spurious Data and Dropouts

Every effort will be undertaken to minimize missing data. In time-to-event outcomes, dropouts will be censored at the time of discontinuation, consistent with the Kaplan-Meier approach. Unless otherwise specified, no statistical techniques will be used to impute missing data. The number of subjects included in each analysis will be reported so that the reader can assess the potential impact of missing data. To evaluate the potential impact of missing data on study results, sensitivity analyses will be performed for the primary endpoints which will include a tipping point analysis.

In the case of partial dates, if only the month and year are known, the event or assessment will be analyzed as if it occurred on the 15th of that month. If only the year is known, the event or assessment will be analyzed as if it occurred on June 30th of that year. Imputation of partial dates is subject to the restriction that pre-implant events must occur between the date of informed consent and the date of implant and post-implant events must occur after the date of implant and prior to date of study exit.

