- Complete case analysis based on the difference in binomial proportions with p-value calculated using a large sample test. This will be run including subjects with events within the timeframes described above for the primary analysis or with evaluable core lab echo (requires evaluable data for all three of: effective orifice area, mean gradient, and aortic regurgitation) free of BVD at 12 months.
- Non-parametric time to first event analysis estimating the cumulative incidence of the valve function composite endpoint while accounting for the competing risk of mortality, with endpoints and event times defined the same way as the primary analysis.
- Non-parametric survival analysis accounting for interval censoring, with the right boundary defined as the earliest event occurrence and the left boundary defined as the last day free of the valve function composite. The event rate estimates corresponding to the interval containing 365 days for each group will be reported, along with the hazard ratio comparing the groups and the p-value for the generalized log-rank test
- Survival analysis accounting for both interval-censoring and competing risk of mortality using the method described by Delord and Génin⁽⁷⁾. As above, the event rate estimates for each group at 365 days will be reported along with a hazard ratio comparing the groups and corresponding significance test.

Revision 5.0

Form

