- Valve-related dysfunction (mean aortic valve gradient \geq 20 mmHg, EOA \leq 0.9-1.1 cm² and/or DVI <0.35m/s, AND/OR moderate or severe prosthetic valve regurgitation)

Page 23 of 27

Note that the EOA threshold of 0.9 applies for subjects with BSA <1.6 m² and EOA threshold of 1.1 applies for subjects with BSA \geq 1.6 m². The endpoint will be evaluated at each time point using the point estimates from a Kaplan-Meier analysis. Components of the endpoint will be reported on the echo core lab CRF, the follow-up visit CRF, and the CEC CRF. Events occurring within 12 months and annually to 5 years, will be counted towards the event rate at each time point. Time to event for the overall composite will be based on the earliest component event; components of the event (NYHA class, valve-related dysfunction) that are detected on scheduled follow-up visits (e.g., 12 months) will be the minimum of the assessment date or the visit target date (e.g., 365 days). Censoring time will be the last available time where subjects are known to be fully event free. Subjects with an event within 30 days will be excluded from the analysis. Analysis of the endpoint will use the Implanted analysis set.

5. Components of the primary clinical endpoint at 12 months and annually to 5 years:

- Mortality •
- **Disabling stroke** •
- Heart failure rehospitalization

Mortality, disabling stroke, and heart failure rehospitalization will be adjudicated by the CEC and analysis will be based on data collected on the CEC adjudication form. Each component will be analyzed with Kaplan-Meier survival analysis according to Section 7.2 for each time point. Analysis of the endpoint will use the AT analysis set.

6. New pacemaker implantation rate at 30 days, 12 months and annually to 5 years

New pacemaker implantation will be reported according to data reported by the investigator on the Permanent Pacemaker Implant CRF. The endpoint will be analyzed with Kaplan-Meier survival analysis according to Section 7.2 for each time point. Analysis of the endpoint will use the AT analysis set, excluding patients with PPI or ICD prior to the study TAVR procedure.

7. Aortic valve re-intervention at 30 days, 12 months and annually to 5 years

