The endpoint will be derived following the same principles as described for the valve function composite co-primary endpoint in **Section 7.9.2**, with same method used for the primary analysis at 12 months. Cutoff days for point estimates are 730, 1095, 1465, and 1825 for analysis time points of 2 years, 3 years, 4 years, and 5 years, respectively. Time to event for events detected on scheduled follow-up echos at 2 years, 3 years, 4 years, and 5 years will be the minimum of the echo date or the visit target date (e.g., 365 days). As in the primary endpoint analysis, HSVD and NSVD events detected through the maximum of the annual visit echo date or the end of the corresponding visit window will be counted to ensure inclusion of events detected on unscheduled echos. Thrombosis, endocarditis, and aortic valve re-intervention events detected through the visit target date (730, 1095, 1465, and 1825 days respectively) will be counted. Components of the endpoint will also be reported at each time point. Analysis will use the Implanted analysis set.

Given the increasing impact of mortality on availability of the BVD endpoint at later time points, a survival analysis for interval-censored outcome data in the presence of competing risks will be performed as a supportive analysis, as described in the list of supportive analyses at the end of **Section 7.9.2**.

11. Echocardiographic measurements (i.e., EOA, mean gradient, PVL, LV mass regression, and DVI (severe <0.25, moderate 0.25-0.5, mild >0.5)) at discharge, 30 days, 12 months and annually to 5 years

Echocardiographic measurements will be summarized descriptively based on core lab reported data at each time point within arm. Analysis will be performed using the Implanted analysis set.

EOA and mean gradient will be analyzed as continuous data. Change from baseline in EOA and mean gradient will be summarized descriptively within each arm. Paravalvular leak (PVL) and DVI (severe <0.25, moderate 0.25-0.5, mild >0.5) will be analyzed descriptively as categorical data.

12. Mean gradient ≥ 20 mmHg based on stress echocardiogram at 12 months at select sites

Mean gradient \ge 20 mmHg based on stress echocardiogram at 12 months will be summarized descriptively as categorical data for each treatment arm. Stress echocardiogram will only be

SMART Trial Statistical Analysis Plan	Form
Revision 5.0 Page 25 of 27	Medtronic

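### SAP 7.10 calls a Kaplan-Meier rate 'cumulative incidence' although deaths are censored, so non-fatal event rates are overstated in the later years

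*SAP*

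**What the plan says.** SAP 7.10 sets the horizon for the safety summary: "CEC adjudicated adverse events will be summarized at 30 days, 1 year, and annually through 5 years". For those summaries, "the Kaplan-Meier event rate (cumulative incidence) will be reported for each category and time point by treatment arm". Counts of events and of subjects with an event are reported beside that rate.

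Three non-powered secondary endpoints in SAP 7.9.4 use the same estimator to 5 years. For endpoint 5 (mortality, disabling stroke, heart failure rehospitalization) the SAP says "Each component will be analyzed with Kaplan-Meier survival analysis according to Section 7.2 for each time point". For endpoints 6 (new pacemaker) and 7 (aortic valve re-intervention) it says "The endpoint will be analyzed with Kaplan-Meier survival analysis according to Section 7.2 for each time point". None of the three is called cumulative incidence.

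SAP 7.2 governs censoring. For subjects without the event, "date of censoring will be based on the latest of all follow-up visits, assessments, and events (for non-death events". SAP 7.4 adds that "dropouts will be censored at the time of discontinuation, consistent with the Kaplan-Meier approach". Neither section gives a rule for competing events.

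The SAP does plan for competing mortality elsewhere. Among the supportive analyses of the 12-month valve function composite, SAP 7.9.2 lists one "estimating the cumulative incidence of the valve function composite endpoint while accounting for the competing risk of mortality". For bioprosthetic valve dysfunction (BVD) at 2 to 5 years, SAP 7.9.4 endpoint 10 adds a supportive competing-risk analysis and gives the reason: "Given the increasing impact of mortality on availability of the BVD endpoint at later time points".

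**The concern.** Cumulative incidence is the proportion of subjects who have had the event by a given time. Someone who dies first can no longer have it. Kaplan-Meier with deaths censored treats that person as still able to have the event later, so 1-KM estimates the proportion that would be seen if nobody died. The two agree only when no one dies before the event. Otherwise 1-KM is the larger, and the gap widens as deaths accumulate.

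The SAP thus gives one term two meanings: in the 7.9.2 supportive analysis it allows for death, and in 7.10 it does not. The handling of re-intervention is also uneven. As a component of BVD at 2 to 5 years it falls under a competing-risk analysis. As endpoint 7 over the same years it does not.

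What is at stake is how the long-term rates of stroke, heart failure rehospitalization, re-intervention and other adjudicated events are read. SAP 4.2 makes 5-year valve function data the trial's secondary objective. A reader who sees a 5-year rate labelled cumulative incidence will take it as the share of patients affected.

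**Working it through.** **The plan's own figure.** The documents state no figure on this point. The non-inferiority sample size in SAP 6 (260 per arm for 80% power, 360 for 90%) reproduces, and it does not depend on the issue because that composite includes all-cause death.

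**Inputs from the documents.** Estimator and label: SAP 7.10. Censoring: SAP 7.2 and 7.4. Horizon: 5 years. Planned size: about 350 per arm (Protocol 7.5).

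**Assumed inputs.** The documents give neither 5-year mortality nor 5-year rates for the events. I take 5-year mortality m from 20% to 50% and a 5-year 1-KM value k of 3%, 10% or 22.1% (the last is a hazard of 0.05 per year). Hazards are constant.

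**Formulas.** Event hazard λ = -ln(1-k)/5; death hazard μ = -ln(1-m)/5.

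- 1-KM at t = 1 - exp(-λt)
- Cumulative incidence at t = λ/(λ+μ) × [1 - exp(-(λ+μ)t)]

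**Worked case, k = 10%, m = 20%.** λ/(λ+μ) = 0.1054/(0.1054 + 0.2231) = 0.3207. The bracket is 1 - 0.90 × 0.80 = 0.28. Cumulative incidence = 0.3207 × 0.28 = 8.98%, an excess of 1.02 points.

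**Worked case, λ = 0.05, m = 50%.** 1-KM = 1 - exp(-0.25) = 22.12%. λ/(λ+μ) = 0.25/(0.25 + 0.6931) = 0.2651. The bracket is 1 - 0.7788 × 0.50 = 0.6106. Cumulative incidence = 16.19%, an excess of 5.93 points.

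**True cumulative incidence at 5 years, with the excess of 1-KM in points:**

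| 1-KM | m = 20% | m = 30% | m = 40% | m = 50% |
|---|---|---|---|---|
| 3% | 2.69 (0.31) | 2.53 (0.47) | 2.35 (0.65) | 2.17 (0.83) |
| 10% | 8.98 (1.02) | 8.44 (1.56) | 7.87 (2.13) | 7.26 (2.74) |
| 22.12% | 19.92 (2.20) | 18.74 (3.38) | 17.50 (4.62) | 16.19 (5.93) |

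In relative terms the overstatement is about 11% at 20% mortality and 37% to 38% at 50%, almost regardless of the event rate.

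**Earlier times.** Under the same assumptions the relative overstatement is 2% to 7% at 1 year and below 1% at 30 days. Even for the 22% event with 50% mortality, the 1-year excess is 4.88% - 4.56% = about 0.3 points.

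**Early events.** Take an event like pacemaker implantation, assumed at 12% in the first 30 days and 1% per year after. The 5-year 1-KM is 16.24%, against a cumulative incidence of 15.78% (m = 20%) to 14.98% (m = 50%). The excess is 0.5 to 1.3 points, or 3% to 8% relative.

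**Simulation check.** With 350 subjects per arm, 400 replicates and a 10% event, Kaplan-Meier with deaths censored averaged 10.0%, 9.9% and 10.0% at 20%, 40% and 50% mortality. Aalen-Johansen averaged 9.0%, 7.8% and 7.3%. The relative excess of 11%, 27% and 38% agrees with the formulas.

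**The case against.** The strongest reply is that little depends on this. SAP 7.9.4 makes endpoints 5 to 7 descriptive, and 7.10 is a summary, so no test, alpha, power or success criterion moves. SAP 7.10 also reports the number of subjects with each event, and 7.2 the number at risk, so a careful reader has other figures to set beside the rate. Many events may be uncommon, and for a 3% event the excess stays below one point. The parenthesis in 7.10 might mean only that the event rate is shown rather than the event-free rate. Censoring of deaths is inferred from 7.2, not stated outright. Aalen-Johansen has its own trap, since an arm with more deaths can show fewer non-fatal events.

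Most of this stands, and it limits the point. It does not rescue the label: counts printed beside a mislabelled percentage do not correct it, and the SAP offers no handling of deaths other than censoring. The reason given for BVD, availability of an endpoint that depends on echo, differs somewhat from the reason here. But 7.9.2 names mortality as a competing risk in so many words.

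A reader might infer three stronger things, which the documents do not support:

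- **That all Kaplan-Meier rates in the SAP are wrong.** For mortality, and for the primary clinical, early safety and clinical efficacy composites, death is itself an event, so there is no competing death.
- **That the rates will be several points too high.** That needs an event near 22% at 5 years, and no document gives such a rate for any listed outcome.
- **That the comparison between arms is biased.** If event hazards were equal (0.05 per year) and 5-year mortality were 20% in one arm and 35% in the other, 1-KM would show 22.1% in both while the cumulative incidences were 19.9% and 18.1%. Nothing in the documents predicts such a mortality gap, and SAP 6 assumes equal composite rates. With similar mortality, both arms are inflated by a similar ratio.

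**Conclusion.** The point holds in a narrow form. In SAP 7.10 the label is wrong for non-fatal events. In 7.9.4 it is the method that matters, for disabling stroke and heart failure rehospitalization in endpoint 5 and for endpoints 6 and 7, none of which carries the label. The direction of the error is a mathematical property once deaths are censored, and needs no assumption about rates.

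The size does rest on assumptions: constant hazards, 5-year mortality of 20% to 50%, and chosen event rates. The documents give no age distribution either; the nearest guides are the subgroup cut at 75 years, the expected mix of 60% intermediate and 20% high surgical risk, and the exclusion of life expectancy below 2 years. On those assumptions the error matters mainly in years 3 to 5.

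The same parenthetical label appears at 12 months in SAP 7.9.1, 7.9.2 and 7.9.5. The clinical composite includes death. The valve function composite has its own competing-risk supportive analysis in 7.9.2. Those uses are outside this point.

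**What to change.** 1. In SAP 7.10, stop calling the Kaplan-Meier rate cumulative incidence for non-fatal categories. Label it *Kaplan-Meier estimate, deaths censored*.
2. For non-fatal events in 7.10, and for 7.9.4 endpoints 5 (disabling stroke and heart failure rehospitalization), 6 and 7, add the Aalen-Johansen cumulative incidence by arm at 2, 3, 4 and 5 years, with death as a competing event. This extends the competing-risk approach already planned for BVD.
3. Keep the Kaplan-Meier estimate beside it for comparability, and leave Kaplan-Meier unchanged for mortality and for composites that include all-cause death.
4. State in SAP 7.2 that deaths before a non-fatal event are censored in the Kaplan-Meier analyses, so that the handling is explicit. Read the new column with the mortality rates, which endpoint 5 already supplies.

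The cost is one extra column in the tables and a short SAP clarification. No new data are needed, and no test or sample size changes. The Aalen-Johansen rates will be less comparable with older reports that used 1-KM, which is why the Kaplan-Meier figure should stay.

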7.11 Stress Echocardiogram Sub-study

A subset of subjects will undergo a stress echocardiogram at selected sites. Demographic, baseline, and treatment characteristics will be summarized descriptively by arm for this cohort. In additional to non-powered secondary endpoint #12, additional parameters collected from the stress echocardiogram may be summarized descriptively including PPM, LV diastolic function, severity of MR, and LVOT obstruction during exercise.

Medtronic

7.12 Changes/Clarification to Planned Analysis

This analysis plan is consistent with the CIP for which the plan was developed with the following clarifications:

Revision 5.0

7.1.3.1 Screening Population. The CIP states that subjects consented who exit prior to the TAVR procedure will not be analyzed or reported. However, the screening population was revised in the SAP to state that subjects who are consented and exited prior to randomization will not be reported as analyses of the ITT population are planned, which will include all randomized subjects including those who exit the study between randomization and the TAVR procedure.

7.9.4 Non-Powered Secondary Objective #1 (Device Success). The CIP states that Device Success will be analyzed on the AT analysis set. The SAP has clarified that this endpoint will be analyzed for patients in the AT analysis set in which the delivery catheter was introduced, since the intended performance component cannot be assessed otherwise.

7.9.4 Non-Powered Secondary Objective #4 (Clinical Efficacy). The CIP states that Clinical Efficacy will be analyzed on the AT analysis set. This has been revised in the SAP to clarify that this endpoint will be analyzed in the Implanted analysis set, since the valve dysfunction component contains echo-derived components which are analyzed using the Implanted analysis set.

Any other deviations from the planned analysis in the CIP will be documented in an amended statistical analysis plan, when possible, and/or will be described with justification and rationale in the study report.

Validation Requirements 8.

Level 1 validation (independent validation) will be used for the analysis datasets and for all hypothesis tested endpoints (co-primary endpoints and five powered secondary endpoints). Level 2 validation (peer review), at minimum, will be used for additional analyses, data summaries, and listings.

9. References

